### 13.1.1 Analysis of Primary Endpoint

Time to progression (TTP) is defined as the time from protocol therapy initiation until documented progression, censored at date last known progression-free for those who have not progressed. At time of final analysis, the 2-year progression-free rate will be estimated using the Kaplan-Meier method with 90% confidence interval per Arm. All patients who have received one dose of study treatment will be included for the TTP analysis, including those who die or are lost to follow-up within 2 years.

The percent of patients who undergo stem cell mobilization and the modality of mobilization will be noted in the study. These patients will not be censored.

### 13.1.2 Analysis of Secondary Endpoints

The objective response rate (partial response or better according to the modified IMWG criteria) and the proportion of patients with a MRD, CR, PR or MR will be reported by Arm with 90% exact binomial confidence interval (CI). The exact 90% CI around response rate will be no wider than 28% with 39 eligible patients.

To estimate the duration of response (time from objective response to disease progression or death, or date last known progression-free and alive for those who have not progressed or died), progression-free survival (time from protocol therapy initiation to the disease progression or death from any cause, censored at date last known progression free for those who have not progressed or died), and overall survival (time from protocol therapy initiation to death or date last known alive), the Kaplan-Meier method will be used. The results will be reported separately for each Arm.

CONFIDENTIAL

This document is confidential. Do not disclose or use except as authorized.

Safety analysis will be conducted using the Safety Population defined as any patient receiving one dose of study treatment. For toxicity reporting, all adverse events and laboratory abnormalities will be graded and analyzed using CTCAE version 4 as appropriate.

### **13.2 Sample Size, Accrual Rate and Study Duration**

A total of 55 patients will be enrolled. We expect 3.5 years of active accrual (approximately 2 patients per month) and 3 years of follow-up of patients.

The final analyses of progression-based endpoints, such as estimating the 2-year progression-free rate and estimating the TTP distribution, will be conducted at the end of the study, which will occur after either all subjects have progressed or died or 2-years after the initiation of therapy of the last subject enrolled, whichever occurs first.

### **13.3 Stratification Factors**

The patients will be stratified based on age and cytogenetics.

- Age 65 years or older
- High risk cytogenetics based on t(4:14), t(14:16), 17p deletion or p53 mutation, +1q amplification (3 groups: high risk, low risk or Fish failure)

### **13.4 Interim Monitoring Plan**

The study will be monitored by the DFCI Data Safety Monitoring Committee (DSMC). The DSMC will meet at least four times a year and more often if needed (e.g., for safety review). For each meeting, the study will be reviewed for safety and progress toward completion. When appropriate, the DSMC will also review interim analyses of the outcome data. Copies of the toxicity reports prepared by the DSMC meetings will be distributed to the Principal Investigator. The Principal Investigator will then distribute to sub-investigators. Any DSMC recommendations for changes to the study will be distributed to the Principal Investigator and then circulated to sub- investigators by the Principal Investigator.

### **13.5 Stopping Rule for Safety**

All participants will be evaluable for treatment-related toxicity from the time of therapy initiation. The severe adverse event (SAE) is defined as any grade 3 adverse events that affect organ function (cardiac, hepatic, thromboembolic) or grade 4/5 non hematologic AEs. We anticipate that the rate of SAE is low in this study population. However, if 2 or more SAEs are observed at any time in the first 20 treated patients in any study cohort, further patient enrollment will be paused for that cohort.

The following table provides the probabilities of observing 2 or more SAEs with 20 treated participants in each cohort. For example, with 20 participants, there is 0.82 probability of observing 2 or more SAEs if a true rate is 15% and the probability is 0.12 if a true rate is 3%.

CONFIDENTIAL

This document is confidential. Do not disclose or use except as authorized.

True SAE Rate	1%	3%	5%	10%	15%	20%	30%
Probability ( $\geq 2$ SAEs)	0.017	0.120	0.264	0.608	0.824	0.931	0.992

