#### 7.1.1.2 Adverse Event List for Lenalidomide

Events that have occurred in >10% of individuals treated with lenalidomide include neutropenia, anemia, thrombocytopenia, fatigue, rash, diarrhea, constipation, nausea, loss of appetite, itching, dry skin, muscle cramps, lack or loss of strength, dizziness, insomnia, swelling of the extremities, headache, back and joint pain, fever, cough, upper respiratory infection, and dyspnea.

Events that have occurred in >1% of individuals treated with lenalidomide include risk of DVT, PE, and blood clots that could lead to stroke, heart attack, or organ failure, febrile neutropenia, atrial fibrillation, pneumonia or lung infections, sepsis, dehydration and renal failure.

Events that have occurred in <1% of individuals treated with lenalidomide include rare treatment-emergent adverse events of angioedema, serious skin reactions including Stevens-Johnson syndrome (SJS) and toxic epidermal necrolysis (TEN) or an allergic skin reaction similar to that seen with thalidomide, tumor lysis syndrome (TLS), tumor flare reaction (TFR), and rhabdomyolysis. In addition, lenalidomide has been shown to increase the level of digoxin in the blood in some patients. Patients will be instructed to inform their doctor if taking digoxin.

There may be an increased risk of second cancers in patients who are on lenalidomide maintenance therapy after a bone marrow transplant.

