## 7.2 Adverse Event Characteristics

- **CTCAE term (AE description) and grade:** The descriptions and grading scales found in the revised NCI Common Terminology Criteria for Adverse Events (CTCAE) version 4.0 will be utilized for AE reporting. All appropriate treatment areas should have access to a copy of the CTCAE version 4.0. A copy of the CTCAE version 4.0 can be downloaded from the CTEP web site [http://ctep.cancer.gov/protocolDevelopment/electronic\\_applications/ctc.htm](http://ctep.cancer.gov/protocolDevelopment/electronic_applications/ctc.htm).
- **For expedited reporting purposes only:**
  - AEs for the agent(s) that are listed above should be reported only if the adverse event varies in nature, intensity or frequency from the expected toxicity information which is provided.
  - Other AEs for the protocol that do not require expedited reporting are outlined in the next section (Expedited Adverse Event Reporting) under the sub-heading of Protocol-Specific Expedited Adverse Event Reporting Exclusions.
- **Attribution of the AE:**
  - Definite – The AE is *clearly related* to the study treatment.
  - Probable – The AE is *likely related* to the study treatment.
  - Possible – The AE *may be related* to the study treatment.
  - Unlikely – The AE is *doubtfully related* to the study treatment.
  - Unrelated – The AE is *clearly NOT related* to the study treatment.

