## 7.4 DF/HCC Expedited Reporting Guidelines

Investigative sites within DF/HCC and DF/PCC will report SAEs directly to the DFCI Office for Human Research Studies (OHRS) per the DFCI IRB reporting policy.

Other investigative sites will report SAEs to their respective IRB according to the local IRB's policies and procedures in reporting adverse events. A copy of the submitted institutional SAE

CONFIDENTIAL

This document is confidential. Do not disclose or use except as authorized.

form should be forwarded to the Overall PI within the timeframes detailed in the table below.

DF/HCC Reportable AEs					
Attribution	Gr. 2 & 3 AE Expected	Gr. 2 & 3 AE Unexpected	Gr. 4 AE Expected	Gr. 4 AE Unexpected	Gr. 5 AE Expected or Unexpected
Unrelated Unlikely	Not required	Not required	5 calendar days #	5 calendar days	24 hours*
Possible Probable Definite	Not required	5 calendar days	5 calendar days #	5 calendar days	24 hours*

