##### 12.1.2 Responsibility for Data Submission

Investigative sites within DF/HCC or DF/PCC are responsible for submitting data and/or data forms to the QACT according to the schedule set by the QACT. Data should be entered within 14 business days of the corresponding visit and within 14 business days of the end of a cycle for any forms to be completed per cycle.

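### The 13.5 enrolment pause does not count a Grade 5 hematologic event, and some of its Grade 3 triggers have no expedited route to whoever keeps the count

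*Combined protocol and SAP*

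**What the plan says.** Section 13.5 defines its event, which it calls a severe adverse event and abbreviates SAE, as "any grade 3 adverse events that affect organ function (cardiac, hepatic, thromboembolic) or grade 4/5 non hematologic AEs". The definition itself sets no limit on expectedness or seriousness. The rule reads "if 2 or more SAEs are observed at any time in the first 20 treated patients in any study cohort", and the action is that "further patient enrollment will be paused for that cohort". The operating characteristics are given in the text as "with 20 participants, there is 0.82 probability of observing 2 or more SAEs if a true rate is 15% and the probability is 0.12" at a 3% rate, followed by a table for seven rates.

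Section 7 governs how events travel:

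- In the 7.4 table, the column "Gr. 2 & 3 AE Expected" is marked as not required in both attribution rows. Unexpected Grade 2 or 3 events are due in 5 calendar days if at least possibly related, and are not required otherwise. Grade 5 events are due in 24 hours.
- Section 7.2 says, for expedited reporting, that listed events "should be reported only if the adverse event varies in nature, intensity or frequency from the expected toxicity information" provided.
- The lenalidomide events listed in 7.1.1.2 as occurring in more than 1% "include risk of DVT, PE, and blood clots that could lead to stroke, heart attack, or organ failure", and also atrial fibrillation. Section 7.1.1.3 lists heart failure, and again DVT or PE, for dexamethasone.
- Section 7.3 sends any serious adverse event to the Overall PI, whatever its grade or expectedness.
- Section 7.9 sends all adverse events to the Overall PI on toxicity forms. Section 12.1.2, on DF/HCC and DF/PCC sites, sets the timing: "Data should be entered within 14 business days of the corresponding visit and within 14 business days of the end of a cycle".
- Section 12.2 lists what the DSMC may receive. It names unexpected events of Grade 2 or higher and deaths within 30 days of intervention. Expected Grade 3 events are not named.

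**The concern.** An enrolment pause protects patients only if the right events are counted and the count is known while patients are still entering. Section 13.5 is the plan's only numeric safety boundary, and it falls short on both.

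The limb that ends in Grade 4/5 excludes hematologic events. Leaving out Grade 4 cytopenias is understandable with this regimen: Section 2.9.5.1 reports Grade 3 to 4 neutropenia in 36% and thrombocytopenia in 21% with the same combination. The same words also leave out a hematologic death, and no reason is given. Section 6.2 puts neutropenia with fever and thrombocytopenia under hematologic toxicities, so a death coded to either would fall outside the count.

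The Grade 3 limb names cardiac and thromboembolic events. Several of these are listed as expected and so fall in the cells of the 7.4 table that need no expedited report. The plan does not say who keeps the running count or from which data.

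**Working it through.** **1. The plan's own table.** Inputs from 13.5: n = 20, threshold 2. Each patient is treated as having an event or not. P(X ≥ 2) = 1 − (1 − p)^20 − 20p(1 − p)^19.

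| True rate | 1% | 3% | 5% | 10% | 15% | 20% | 30% |
|---|---|---|---|---|---|---|---|
| Stated | 0.017 | 0.120 | 0.264 | 0.608 | 0.824 | 0.931 | 0.992 |
| Recomputed | 0.0169 | 0.1198 | 0.2642 | 0.6083 | 0.8244 | 0.9308 | 0.9924 |

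All seven cells agree.

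**2. Triggers set against reporting routes.**

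| Event | Counted in 13.5? | DF/HCC expedited report (7.4) |
|---|---|---|
| Grade 5 hematologic | No | 24 hours |
| Grade 5 non-hematologic | Yes | 24 hours |
| Grade 3 DVT, PE, atrial fibrillation, heart failure (listed) | Yes | Not required |
| Grade 3 cardiac, hepatic or thromboembolic, unexpected, unrelated or unlikely | Yes | Not required |
| Grade 3 hepatic (none listed in 7.1), at least possibly related | Yes | 5 calendar days |

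The first row is reported but not counted. The third and fourth are counted but not expedited, unless the event is also serious under 7.3.

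**3. Size of the delay.** Fourteen business days is about 20 calendar days. The Section 10 calendar notes toxicity on Day 1 of each cycle, so an event just after Day 1 may wait 27 days; the worst case is 27 + 20 = 47 days. Section 13.2 gives two accrual rates: about 2 per month, and 55 patients over 42 months, which is 55/42 = 1.31 per month. Further patients enrolled = rate × days / 30.44.

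| Delay | At 1.31 per month | At 2 per month |
|---|---|---|
| 5 days (existing expedited route) | 0.2 | 0.3 |
| 20 days (entry only) | 0.9 | 1.3 |
| 47 days (worst case) | 2.0 | 3.1 |

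Delay changes when the count is known, not whether two events occur. Nothing in the plan says that events would be lost, so no under-capture factor is applied.

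**4. The rule while enrolment is open.** Assumptions: patient i enters at (i − 1)/a months, where a is the accrual rate; treatment lasts 24 × 28 = 672 days, or 22.08 months; events are spread evenly over treatment. Enrolment closes at T = 55/a. Patient i contributes probability p × min(1, [T − (i − 1)/a]/22.08).

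- At 2 per month, T = 27.5. Patients 1 to 11 have completed treatment, and patient 20 has (27.5 − 9.5)/22.08 = 82% of it. The pause probability is about 0.58 at a 10% rate and 0.80 at 15%.
- At 1.31 per month, T = 42. All 20 have completed treatment, so the tabulated 0.61 and 0.82 apply.

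**5. Patients 21 to 55.** These are 35 of 55 (64%). Expected patients with an event: 35 × 0.10 = 3.5 and 35 × 0.15 = 5.25. For an illustrative cumulative boundary of 2 of 20, 4 of 40 and 5 of 55:

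| | 10% rate | 15% rate |
|---|---|---|
| Current rule, enrolment open | 0.58 to 0.61 | 0.80 to 0.82 |
| Cumulative boundary, enrolment open | 0.62 to 0.69 | 0.85 to 0.90 |
| Cumulative boundary, complete follow-up | 0.78 | 0.96 |

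Each range runs from 2 to 1.31 patients per month. The cumulative figures with enrolment open are by simulation under the assumptions in step 4.

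**The case against.** The defence is substantial. The table is right, and because events count at any time the first 20 stay under observation after patient 20 has entered. A reader might infer that the rule cannot deliver what its table shows; step 4 does not support that, since the loss by close of enrolment is at most about 0.03. Events concentrated in the more intensive early cycles would reach the count sooner still.

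A reader might also infer that the Grade 3 triggers as a class escape expedited reporting. They do not. Unexpected related events, which include related hepatic events, are due in 5 days. Serious events go to the Overall PI under 7.3 and to the lenalidomide supplier within 24 hours under 7.7. Listed events that differ in intensity or frequency are also reportable, and 7.1 gives no grades for DVT or PE, so some Grade 3 cases may qualify. How many triggers are left cannot be settled from the public text, where the definition of serious is not visible; that is not held against the plan.

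A hematologic death would not go unnoticed. It is reportable within 24 hours, may reach the DSMC, and one death alone would not meet a two-event threshold. A death coded to sepsis or pneumonia would count.

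The DSMC list in 12.2 is permissive rather than exhaustive, and 13.4 provides for meetings at least four times a year. A first-20 rule backed by such review is a legitimate design choice.

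What survives is narrower: being reported is not being counted, and being counted does not ensure prompt reporting.

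**Conclusion.** Two gaps stand on the text alone: a Grade 5 hematologic event is outside the count, and expected, unrelated or unlikely Grade 3 triggers that are not serious reach the Overall PI only by routine forms. The second costs about 20 days for data entry and 47 at worst, or roughly 1 to 3 more enrolments at the two accrual rates in 13.2. The double use of SAE, severe in 13.5 and serious in Section 7, makes it easy for a site to assume that 7.3 covers every 13.5 event.

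Both gaps are worth closing because the repair is cheap. They do not invalidate the rule or its table.

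The absence of a numeric boundary for patients 21 to 55 is a point to consider, not an error. A reader might take 0.78 and 0.96 as the benefit of extending the rule. Those figures assume complete follow-up, after which a pause has nothing left to stop. With evenly spread events, the gain while enrolment is open is about 0.04 to 0.08 at either rate.

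**What to change.** 1. **Definition (13.5).** Keep the Grade 3 limb and replace the rest with: *or grade 4 non-hematologic AEs, or any grade 5 AE*. The chance of a pause rises with the added event rate, which the documents do not give. If it were 0.5 to 1 percentage point (assumed) on top of 3%, the formula in step 1 gives 0.154 to 0.190 instead of 0.120.
2. **Route (13.5, 7.3, 7.4).** Send every event that meets the 13.5 definition to the Overall PI on the existing 5-calendar-day route, whatever its expectedness or seriousness. State who keeps the running count. State also whether events judged unrelated count, because the opening sentence of 13.5 speaks of treatment-related toxicity while the definition sets no such limit. With one event per patient, 55 patients at 10% to 15% give 5.5 to 8.25 events in all, and only some need a form not already required.
3. **DSMC data (12.2).** Add 13.5 events to the items named.
4. **Terms.** Give the 13.5 event its own name, so that SAE means serious adverse event throughout.
5. **To consider.** If a cumulative boundary for patients 21 to 55 is added, state its operating characteristics for the period while enrolment is open, at both 2 and 1.31 patients per month, with the assumed timing of events. It also raises false pauses: for 2 of 20, 4 of 40 and 5 of 55 with complete follow-up, from 0.26 to 0.32 at a 5% true rate.

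Items 1 to 4 need amendment wording only and leave the sample size and primary analysis unchanged.

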## 14. PUBLICATION PLAN

The results should be made public within 24 months of reaching the end of the study. The end of the study is the time point at which the last data items are to be reported, or after the outcome data are sufficiently mature for analysis, as defined in the section on Sample Size, Accrual Rate and Study Duration. If a report is planned to be published in a peer-reviewed journal, then that initial release may be an abstract that meets the requirements of the International Committee of Medical Journal Editors. A full report of the outcomes should be made public no later than three (3) years after the end of the study. Data sets from other relevant studies such as 17-212, 16-313, or data sets from other collaborators may be used and/or analyzed for the purposes of the publication.

CONFIDENTIAL

This document is confidential. Do not disclose or use except as authorized.

## APPENDIX A: PERFORMANCE STATUS CRITERIA

ECOG Performance Status Scale		Karnofsky Performance Scale	
Grade	Descriptions	Percent	Description
0	Normal activity. Fully active, able to carry on all pre-disease performance without restriction.	100	Normal, no complaints, no evidence of disease.
		90	Able to carry on normal activity; minor signs or symptoms of disease.
1	Symptoms, but ambulatory. Restricted in physically strenuous activity, but ambulatory and able to carry out work of a light or sedentary nature (e.g., light housework, office work).	80	Normal activity with effort; some signs or symptoms of disease.
		70	Cares for self, unable to carry on normal activity or to do active work.
2	In bed <50% of the time. Ambulatory and capable of all self-care, but unable to carry out any work activities. Up and about more than 50% of waking hours.	60	Requires occasional assistance, but is able to care for most of his/her needs.
		50	Requires considerable assistance and frequent medical care.
3	In bed >50% of the time. Capable of only limited self-care, confined to bed or chair more than 50% of waking hours.	40	Disabled, requires special care and assistance.
		30	Severely disabled, hospitalization indicated. Death not imminent.
4	100% bedridden. Completely disabled. Cannot carry on any self-care. Totally confined to bed or chair.	20	Very sick, hospitalization indicated. Death not imminent.
		10	Moribund, fatal processes progressing rapidly.
5	Dead.	0	Dead.

CONFIDENTIAL

This document is confidential. Do not disclose or use except as authorized.

## APPENDIX B: PREPARATION AND ADMINISTRATION OF ELOTUZUMAB

### Dose Preparation Instructions

After dilution in normal saline, elotuzumab must be administered within 8 hours if kept at room temperature (25°C). If a delay is anticipated after the dose has been diluted in normal saline, the prepared dose (properly identified) may be refrigerated at 2°C to 8°C for up to 24 hours. If stored under refrigerated conditions, the study drug solution should be equilibrated to room temperature (takes about 2 to 2.5 hours), and the container must be gently inverted to thoroughly mix the contents before administration. If the storage time limit is exceeded, the prepared dose solution must be discarded and the reason documented by the pharmacist in the study drug accountability records.

Elotuzumab will be administered to each subject as an IV infusion, using an automated infusion pump set at the appropriate rate according to the dose administration section (see Administration Instruction section below) discussed below. The dose of elotuzumab will be calculated using the subject's predose weight on Day 1 of each cycle or predose weight at each visit, whichever institutional policy is, and then added to 0.9% saline for infusion. Do not round up or down.

Reconstitute elotuzumab lyophilized study drug, as described in Steps 1 to 5. Each 400 mg vial contains 10% overfill for a total of 440 mg of study drug but is intended to deliver 400 mg of elotuzumab. Standard aseptic technique should be utilized.

Step 1: Remove the flip-top from elotuzumab and Sterile Water for Injection (SWFI) vials.

Step 2: Withdraw 17 mL of SWFI using an 18-gauge or smaller needle. Place the elotuzumab vial upright on a flat surface and insert the syringe needle into the vial through the center of the rubber stopper. Slowly inject the SWFI along the side of the vial to help prevent bubbling or foaming. Slowly remove the syringe needle out of the vial.

Step 3: DO NOT SHAKE. Avoid prolonged or vigorous agitation. Hold the vial upright and gently swirl the solution by rotating the vial to dissolve the lyophilized cake. Then gently invert the vial a few times in order to dissolve any powder that may be present on top of the vial or the stopper. Finally, hold the vial upright again and gently swirl the solution a few more times to dissolve any remaining particles.

Step 4: After the remaining solids are completely dissolved, allow the reconstituted solution to stand for 5 to 10 minutes. The final volume of the reconstituted solution is approximately 17.6 mL, for an approximate concentration of 25 mg/mL.

It is acceptable to have small bubbles and/or foam around the edge of the vial. The reconstituted preparation results in a colorless to slightly yellow, clear to slightly opalescent solution.

Step 5: Once the reconstitution is completed and prior to IV administration, the reconstituted solution is further diluted with 230-340 ml of 0.9% sodium chloride injection (NS), USP, resulting in elotuzumab concentrations between 2 mg/mL and 6.6 mg/mL. The infusion is to be administered through a sterile, non-pyrogenic, low protein binding in-line filter. Additionally,

CONFIDENTIAL

This document is confidential. Do not disclose or use except as authorized.

care must be taken to ensure the sterility of the prepared solution, as the drug product does not contain anti-microbial preservatives or bacteriostatic agents. A sufficient excess of drug product is included in each vial to account for withdrawal losses.

The first dose of elotuzumab will be administered following pre-medications to each subject as an IV infusion, using an automated infusion pump set at an initial rate of 0.5 mL per minute (30 mL/hour). If the subject does not have an infusion reaction within 30 minutes, escalate the infusion rate by 0.5 mL per minute. If the subject still does not have an infusion reaction within 30 minutes, escalate the infusion rate to a maximum of 2 mL per minute (120 mL/hour). If a subject experiences a Grade 2 infusion reaction, the infusion must be interrupted.

The second dose of elotuzumab should be initiated at an infusion rate of 3 mL per minute if no infusion reactions were reported with the first elotuzumab infusion. If the subject does not experience an infusion reaction during the first 30 minutes of the second dose of elotuzumab, escalate the infusion rate by 1.0 mL per minute to a maximum infusion rate of 4 mL per minute.

If no infusion reactions were observed during the first two doses cycle of elotuzumab, the third dose can commence at a rate of 5 mL per minute.

If a patient experiences an infusion reaction of less than or equal to Grade 2, and the infusion reaction does not recur, the patient can resume elotuzumab administration at the rate at which the reaction occurred at the start of the next cycle at the investigator's discretion.

If a subject experiences a Grade 2 infusion reaction, the infusion must be interrupted. Please refer to Section 6.4.2 for detailed information on the management of infusion reaction and re-initiation of infusion. If a subject experiences a Grade 3 elotuzumab infusion reaction that has resolved to Grade 1, subsequent infusion rate of elotuzumab should be escalated in a stepwise fashion (0.5 mL every 30 minutes).

- 1) Administer through a low-protein-binding 0.22-micrometer in-line filter (placed as proximal to the subject as is practical). Prime the infusion line with study drug before starting the infusion.
- 2) Set the IV pump to deliver the infusion at the rate of 0.5mL per minute (including the drug in the line). The total time of infusion will vary depending upon the maximum tolerated mL/min infusion rate as discussed above.
- 3) Record every time the infusion is started and stopped and the reason why the start and stop occurred.
- 4) Monitor the IV setup and the subject's IV site frequently during infusion, checking for the correct infusion rate and IV site infiltration.
- 5) Ensure that the full volume of elotuzumab is infused.

After elotuzumab has been infused from the line, discontinue the infusion, disconnect the IV tubing, and dispose of materials appropriately according to the facility's standard procedure.

CONFIDENTIAL

This document is confidential. Do not disclose or use except as authorized.

